| Study Design | Prospective, randomized, multi-center, comparative effectiveness trial; patients randomized with equal allocation (1:1). Baseline and peri-procedural data collection will be partially extracted from the Society of Thoracic Surgeons (STS) Data Registry. Limited additional data will be collected to assess coronary anatomy, pharmacology specific to the procedure, device usage, etc. When allowed by local IRB/REBs, follow-up data collection, with the exception of data collection at post-intervention clinical visits, will be collected centrally via phone follow-up by the Hybrid Trial Data Coordinating Center (DCC), and will focus on patient-reported MACCE and QOL, supplemented by limited supporting documentation to verify MACCE events, and cost data collected from the University Health Consortium (UHC) and directly from hospitals for non-UHC members. All MACCE events will be adjudicated by a Clinical Events Committee (CEC). The estimated enrollment period is 24 months and all patients (n = 2354) will be followed for 5 years following randomization. |
| Target Population | Patients with multi-vessel CAD involving the LAD distribution with a clinical indication for revascularization and eligible for both HCR and multi-vessel PCI with DES. |
| Rx arms | 
 ○ HCR with sternal-sparing, off-pump Left Internal Mammary Artery (LIMA) to LAD + PCI with metallic drug eluting stents (DES) of non-LAD vessels ○ Multi-vessel PCI with metallic DES, including the LAD and or LM. |
| Sample Size | 2354 patients; assuming an estimated event rate of approximately 25% in the PCI group at 5 years; 0.05 type I error (2-sided) and assuming: (a) minimum follow-up of 5 years, (b) 80% power, (c) drop-in and drop-out rates of approximately 0.5% and 2% respectively, annually, and (d) 15% loss to follow-up by end of the study, 530 events will need to be observed (or 2354 patients) to detect a relative decrease in MACCE of $\geq 20\%$ in the HCR compared to the PCI group. Estimates of loss to follow-up, and cross-over rates are conservative and justify fixing the power at 80%. |
| Duration | Accrual over 2 years; accrual will terminate when 530 events have occurred or 2354 patients are randomized, whichever comes first. All patients will be followed for 5-years. |

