| 1° Endpoints | The occurrence of MACCE defined as all-cause mortality, myocardial infarction (MI), stroke, or unplanned revascularization over 5-year follow-up after randomization or at the time when 530 events have accrued. |
| 2° Endpoints | 
Measured at 30 days post procedure, 12, 24, 36, 48, 60 months, unless otherwise specified:
 
Cardiovascular Events
 
 ○ MACCE at each data collection time point ○ Individual components of MACCE 
 ○ All-cause mortality ○ Unplanned revascularization ○ Stroke ○ Myocardial infarction (MI) ○ Ischemia-driven revascularization ○ Cardiovascular and non-cardiovascular mortality 
Hospitalizations
 
 ○ Re-hospitalization (all-cause and cardiovascular) |

| | |
|---|--|
| | 
Health Status
 
 ○ Angina Score (Canadian Cardiovascular Society Classification [CCSC]) ○ Quality of Life (SF-12 and EuroQOL) 
Cost-effectiveness
 
 ○ Costs |

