months of total follow up (see Figure 1).²³ The study further confirmed that there is strong concordance between cardiac surgeons and interventional cardiologists regarding anatomic eligibility for HCR, with disagreement in only 3.0% of cases.²⁴ Such consensus supports the feasibility of conducting a much needed comparative effectiveness trial of this emerging new coronary revascularization paradigm.

Thus, the NHLBI-funded Hybrid Observational Study demonstrated that equipoise exists between the two coronary revascularization paradigms; however, a rigorously designed randomized clinical trial is now needed to provide sufficient evidence to guide clinical decision making for this important patient population.

STUDY DESIGN

This trial is a prospective, multi-center randomized comparative effectiveness trial of HCR compared to multi-vessel PCI with metallic DES in patients with multi-vessel CAD involving the LAD or LM territories. The trial is designed as a “large, simple” trial, and some baseline, procedure-related and short-term outcomes data collection will be extracted from existing registry data from the Society of Thoracic Surgeons [STS] Data Registry. By incorporating existing clinical data collected by sites for reporting to STS registry, the design greatly reduces trial-specific data collection at the sites participating in STS. When allowed by local Institutional Review Boards (IRBs) or Research Ethics Boards (REBs), follow-up data collection, with the exception of data collection at post-intervention clinical visits, will be collected centrally via phone follow-up by the Hybrid Trial Data Coordinating Center (DCC). All follow-up data collection will focus on patient-reported MACCE events and QOL, and will be supplemented by limited supporting documentation to verify MACCE events. All MACCE events will be adjudicated by a Clinical Events Committee (CEC). Health care costs will be collected

Hybrid Coronary Revascularization Trial electronically through Uniform Billing (UB) medical claim forms and the University HealthSystem Consortium (UHC) operational database system. This design decreases (1) duplication of effort, (2) the burden on participating patients and sites, and (3) the cost of conducting the trial, while maintaining the rigor of traditional RCTs. The estimated enrollment period is 24 months (n = 2354), and all patients will be followed for a minimum of 5 years following randomization.

CONFIDENTIAL

ENDPOINTS

Primary Endpoint

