The primary endpoint of this trial is MACCE over 5 years following randomization. For the purpose of this trial, the components of MACCE include (1) all-cause mortality, (2) myocardial infarction, (3) stroke, and (4) unplanned revascularization. The primary objective of this trial is to determine whether hybrid coronary revascularization is associated with a reduction in MACCE compared to PCI with metallic DES.

Secondary Endpoints

The secondary endpoints of the trial (measured at 30 days post procedure, 12, 24, 36, 48, and 60 months, unless otherwise specified) include:

Cardiovascular Events

- MACCE at 30 days post procedure, and 12, 24, 36, 48 months
- Individual components of MACCE: All-cause mortality, myocardial infarction, stroke, unplanned revascularization
- Ischemia-driven revascularization
- Cardiovascular and non-cardiovascular mortality

Hospitalizations

- Re-hospitalization (all-cause and cardiovascular)

Health Status

- Angina Score (Canadian Cardiovascular Society Classification [CCSC])
- Quality of Life (QoL) (Short Form 12 Health Survey [SF-12}, European Quality of Life Scale [EuroQoL])

Cost-effectiveness

- Costs
- Quality-adjusted life expectancy

STUDY POPULATION

The patient population for this trial consists of adult patients with multi-vessel coronary artery disease involving the Left Main (LM) and/or Left Anterior Descending (LAD) arteries, and a clinical indication for revascularization, who are candidates for both HCR and PCI with metallic DES.

Eligibility Criteria

All patients who meet all inclusion criteria and no exclusion criteria will be eligible for the trial

Inclusion Criteria

1. Signed informed consent, inclusive of release of medical information, and Health Insurance Portability and Accountability Act (HIPAA) documentation (US sites)
2. Age \geq 18 years
3. Clinical indication for coronary revascularization
4. Coronary anatomy requiring revascularization as follows⁽²⁾
 - Multivessel CAD involving the LAD (proximal or mid) *and/or* LM (ostial, mid-shaft or distal) *with* at least 1 other epicardial coronary artery requiring treatment (LCX or RCA), OR
 - Single vessel disease involving the LAD and a major diagonal, with both requiring independent revascularization with at least one stent if randomized to HCR and stents for both the LAD and diagonal if randomized to multivessel PCI

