Only commercially available metallic drug-eluting stents may be used in this protocol. Because the use of DES on patients with left main disease or with three-vessel disease, both of which are off-label uses for DES, is considered investigational, this trial will be conducted under an Investigational Device Exemption (IDE). PCI should be performed using standard techniques at the discretion of the operator. In general PCI should be performed of lesions in vessels with visually estimated reference vessel diameter ≥ 2.25 mm with evidence of a) plaque rupture or thrombosis, or b) with an angiographic diameter stenosis $\geq 80\%$, or c) with evidence of ischemia on either non-invasive testing or by fractional flow reserve ≤ 0.80 or iFR ≤ 0.90 . Which of these criteria are met will be categorized. The specific adjunctive devices used (e.g. atherectomy, cutting/scoring balloons, or aspiration) and techniques (e.g. 1- vs. 2-stent and technique for treatment of bifurcation lesions) will be collected. Bioresorbable vascular scaffolds may not be used in this study.

Procedures may be staged at the discretion of the operator, but the intention to stage procedures must be specified within 24 hours after completion of the first procedure, should ideally be completed within 60 days of the first procedure, and in all cases must be completed within 90 of the first procedure after randomization.

For patients randomized to HCR, if off-pump CAB is performed first, prior to the staged PCI procedure a diagnostic angiogram of the LIMA-LAD graft must be performed, irrespective of the

Optimal Medical Management

All patients should be managed according to guideline-directed medical therapy (GDMT) by clinicians at each clinical site according to generally accepted societal recommendations. Details of GDMT are included in the MOP. Information will be collected about adherence to GDMT.

DEFINITIONS AND MEASUREMENT OF ENDPOINTS

Primary Endpoint

The primary endpoint for this trial is a composite of MACCE over 5 years following randomization.

All MACCE events will be adjudicated by an independent CEC. For the purpose of this trial **MACCE** is defined as a non-weighted composite score comprised of the following components:

- *All-cause mortality*
Death from any cause
- *Stroke*

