Sample size for this study was determined based on the following operating characteristics: (a) two sided type I error fixed at 0.05, (b) 80% power, (c) minimum follow-up of 5 years, 2-year enrollment period with uniform enrollment (d) 5-year MACCE rate in the PCI group of approximately 25%, (e) expected 5-year MACCE relative rate reduction in the HCR group of $\geq 20\%$, (f) drop-in (HCR to PCI) and drop-out (PCI to HCR) rates of approximately 0.5% and 2% respectively, and (g) loss to follow-up by the end of the study of 15%. Under the above assumptions it is estimated that 530 events (or 2354 patients) will be required to detect a relative decrease in MACCE of $\geq 20\%$ in the HCR compared to the PCI group. This is a reasonable improvement based on estimates from recent studies.²⁵⁻²⁸

Interim Monitoring Guidelines

The objectives of interim monitoring are to (1) monitor for safety, (2) track participant accrual rates, and (3) monitor the primary and secondary outcomes for early evidence of efficacy, harm or futility. To accomplish this, summaries of data quality, accrual, adherence, distribution of

baseline factors, safety, study endpoints and other analyses as requested will be prepared for review by the DSMB. A single interim analysis and one final analysis are planned for this trial, for a total of two analyses. The interim analysis will be conducted when 0.5 fraction of the total number of events have been observed. This interim analysis will evaluate the composite rate of adjudicated death, stroke or MI (excluding unplanned repeat revascularization), as the endpoint is being conducted for safety, rather than efficacy, purposes. We will use an alpha-spending O'Brien-Fleming sequential procedure as a guideline for decision-making. At the interim analysis the value of the test statistic will be compared with the alpha spending function critical value. The p-values for the interim monitoring analysis and the final analysis are, 0.0031, and 0.05, respectively.

Stopping Rule

We do not anticipate stopping the trial for evidence of early efficacy or futility at the time of the interim analysis. The collection of 5-year follow-up information on all patients enrolled in the trial is necessary to provide a comprehensive overview of the relative safety and effectiveness of the two randomized strategies.

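### The plan gives incompatible ends of follow-up for the primary endpoint, and whether 2354 patients give 80% power depends on which end applies and on an unsettled crossover unit

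*Combined protocol and SAP*

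**What the plan says.** Three ends of follow-up appear in the current text.

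- **Five years.** The Endpoints section: "The primary endpoint of this trial is MACCE over 5 years following randomization". Definitions and Measurement of Endpoints: "The primary endpoint for this trial is a composite of MACCE over 5 years following randomization". The Abstract, Study Design row: "all patients (n = 2354) will be followed for 5 years following randomization". The Data Collection Schedule and the long-term follow-up section place the last scheduled call at 60 (±1) months.
- **At least five years.** The Study Design section: "all patients will be followed for a minimum of 5 years following randomization". The Abstract's sample-size row lists "a) minimum follow-up of 5 years, (b) 80% power, (c) drop-in and drop-out rates of approximately 0.5% and 2% respectively, annually". Power and Sample Size uses the same minimum with 2-year uniform enrollment. The opening of the Analytical Plan and Analysis of Primary Endpoint also use a minimum of 5 years, and censor event-free patients at the end of the study, which is not defined.
- **An event count.** The Abstract's primary endpoint row: "over 5-year follow-up after randomization or at the time when 530 events have accrued". No rule says which end prevails.

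The Abstract's Duration row uses the same count to end recruitment: "accrual will terminate when 530 events have occurred or 2354 patients are randomized, whichever comes first. All patients will be followed for 5-years".

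Power and Sample Size concludes: "Under the above assumptions it is estimated that 530 events (or 2354 patients) will be required to detect a relative decrease in MACCE". It gives the 0.5% and 2% crossover rates with no time unit, whereas the Abstract calls them annual.

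**The concern.** With a common closing date, 2-year uniform accrual and a 5-year minimum give each patient 5 to 7 years of observation. A 60-month endpoint gives each patient exactly 5. The documents support both, so a programmer cannot tell whether a first event at month 66 in an early enrollee counts or is censored away. If it counts, no scheduled call would find it; only event-driven reporting by the patient remains.

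The choice also changes the number of events available to the log-rank test, and so possibly the power. It affects the interim look as well, which is set at half of a total event count: 265 if that total is 530.

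**Working it through.** **Inputs.** Two-sided 0.05, 80% power, 1:1 allocation, 2-year uniform accrual, a 5-year MACCE rate of 25% on PCI, a 20% relative reduction, and 15% loss by the end of the study (Power and Sample Size). Crossover is 0.5% and 2% per year (Abstract).

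**Assumptions.** The reduction applies to the 5-year rate, so 25% falls to 20%. Loss is exponential censoring that reaches 15% by year 5 or by year 7. Crossover is run in the labelled direction and reversed. Ranges cover these four combinations.

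**Hazards.** PCI: −ln(0.75)/5 = 0.0575 per year. HCR: −ln(0.80)/5 = 0.0446 per year. Hazard ratio 0.0446/0.0575 = 0.776. Loss: −ln(0.85)/5 = 0.0325, or −ln(0.85)/7 = 0.0232.

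**Starting point without crossover.** Events needed = 4(1.960 + 0.842)²/[ln 0.776]² ≈ 487. Crossover pulls the hazard ratio toward 1 (to about 0.79 with annual rates) and raises this number.

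**The plan's patient number.** A Markov log-rank calculation of the Lakatos type, with annual crossover and a common close when the last patient reaches 60 months, needs 2,276 to 2,354 patients for 80% power. The stated 2354 is therefore reproduced.

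**The plan's event number.** 530 does not come out of that model as the requirement. Two readings come close as expected counts:

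- 60 months with no loss and no crossover: 2354 × (0.25 + 0.20)/2 = 529.65.
- 5 to 7 years with 15% of patients removed at the outset: 524–529.

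The documents do not say how loss was applied, so the origin of 530 cannot be established.

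**Results at 2354 patients, annual crossover, gradual loss:**

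| End of follow-up | Expected events | Power | Patients for 80% |
|---|---|---|---|
| Common close, 5–7 years | 563–583 | 80–81% | 2,276–2,354 |
| 60 months for each patient | 489–503 | 75–76% | 2,578–2,654 |

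The difference in events is the 74–80 first events after month 60, about 13–14% of the common-close total (74/563 to 80/583). Under either rule 80% power needs about 546–570 events, and exactly 530 gives about 77–79%. Simulation agreed: 74–76% at 60 months and 79–82% with a common close.

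**Sensitivity to crossover.** If 0.5% and 2% are totals over 5 years, the 60-month endpoint gives about 79–80% power, needs about 2,354–2,409 patients for 80%, and needs only about 501–505 events. Exactly 530 events then gives about 82%.

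**Sensitivity to the control rate.** With annual crossover and a PCI rate of 27%, the 60-month endpoint yields about 528–544 events and 79–80% power.

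**Sensitivity to the effect scale.** If the 20% reduction is read as a hazard ratio of 0.80 with annual crossover, power is about 65% at 60 months and 70–71% with a common close.

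**Accrual stop.** With uniform entry over 2 years, the expected proportion with an event by month 24 is 1 − (1 − e^(−2λ))/(2λ): 0.0555 on PCI and 0.0433 on HCR. With 1177 per arm that is 1177 × (0.0555 + 0.0433) ≈ 116 events, or about 114 after loss. That is far below 530.

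**The case against.** A reader might infer that 80% power holds only with 5 to 7 years of follow-up, and that 530 events is simply too few. The documents do not support either statement outright. Power and Sample Size gives crossover without a time unit. Read as cumulative, a 60-month endpoint comes within about a point of 80%, the stated 2354 can again be reproduced, and 530 events is more than enough. The Abstract does say annual, which makes that reading the better supported one, but it does not exclude the other in the section that reports the calculation.

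Nor should 563–583 be set against 530 as though they were the same quantity. The first is the count expected at 2354 patients under an assumed loss model; the second is stated as a requirement. The comparable requirement with annual crossover is about 546–570.

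It would also go too far to say that the primary endpoint stops at 5 years. The Analytical Plan defines it over a minimum of 5 years, and that disagreement is the point.

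Finally, the power difference is modest, the control rate is only approximate, and the Abstract describes its loss and crossover rates as conservative. All of this stands. It limits the claim about power. It does not settle when follow-up ends, which is a conflict of wording that needs no model to see.

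**Conclusion.** The contradiction in the endpoint window is established from the text alone. It determines whether about 74–80 expected first events enter the primary analysis, and under the longer window no scheduled contact would collect them.

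The effect on power is conditional. With annual crossover, gradual 15% loss and 25% versus 20%, it is about 80–81% under a common close against 75–76% under a 60-month endpoint. It largely disappears if crossover is cumulative or the PCI rate is about 27%. A flat conclusion that the trial is underpowered, or that 530 is an arithmetic error, is not supported, because the crossover unit is inconsistent and the treatment of loss is not stated.

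Separately, 530 events cannot work as a stop on a 2-year accrual when only about 114 are expected by month 24.

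**What to change.** Choose one end of follow-up and use it in the endpoint, schedule, power and analysis sections.

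- **(a) 60-month endpoint.** Censor at 60 months and remove the minimum-of-5-years wording from the Abstract, Study Design and Analytical Plan. This costs wording only. With annual crossover and gradual loss, the stated power would be about 75–76%.
- **(b) Common close when the last patient reaches 60 months.** Change the over-5-years definitions, define the end of the study, and add 6-monthly calls at up to 66, 72, 78 and 84 months. Under uniform accrual, patients enrolled at least 6 months before the last one need at least one added call: 18/24 = 75%, or about 1,765 patients. On the same inputs, power would be about 80%.

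Under either option:

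- Make the crossover unit in Power and Sample Size match the Abstract, and state how loss was applied.
- Have the sponsor rerun its own calculation and restate events and power together at 2354. The figures here depend on the loss model and should not be copied in.
- Remove 530 events as an accrual stop.
- Delete the event clause from the Abstract's primary endpoint, or state which end prevails.
- Base the half-information interim look on the restated total.

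The number of patients does not change. The choice should be made without reference to comparative outcome data.

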Randomization

Must be completed

- (a) within 90 days of the 3-vessel qualifying angiogram for patients identified in the setting of a diagnostic angiogram, or*
- (b) within 90 days following the qualifying 3-vessel angiogram for patients also undergoing a PCI of a non-LAD and non-LM vessel prior to randomization. (See table under Randomization Section)*

The first study intervention is recommended to be performed within 72 hours post randomization and must be performed within 14 days following randomization.

Randomization to the treatment assignment will be generated by the EDC system once the checklist of inclusion and exclusion criteria has been completed and verified and the planned revascularization strategy form has been completed. For the purpose of the primary analysis, patients are considered enrolled in the study once they are randomized and an identification code is generated.

Revascularization Plan

Prior to randomization

The surgical and percutaneous revascularization plan will be described for both HCR and PCI-only revascularization *prior to randomization*. This plan may be revised within 24 hours of the first procedure after randomization to reflect procedural complications, should they occur. Any revascularization procedures deviating from the final revascularization plan in place 24 hours after the first procedure will be considered unplanned revascularization procedures.

Note: Any revascularization procedure that is done during a planned revascularization procedure will NOT be considered an unplanned procedure. E.g.: planned minimally invasive LIMA-LAD procedure becomes complicated by inferior ischemia requiring conversion to an open procedure and RCA bypass; or planned PCI after minimally invasive

LIMA-LAD procedure demonstrated LIMA-LAD graft occlusion requiring PCI; or planned PCI of the LCX results in a LM dissection requiring a LM stent. However, CABG complications that result in separate **unplanned** PCI or CABG procedures, and PCI complications that result in separate **unplanned** PCI or CABG procedures, will be considered unplanned procedures and endpoint events.

Angina Class - Canadian Cardiovascular Society Classification (CCSC)

Following determination of eligibility and within 14 days prior to randomization

The presence of angina will be assessed, and when present, classified according to the CCSC scale and documented on this form. CCSC classification scheme is detailed in Appendix I.

NYHA Class

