Following determination of eligibility and within 14 days prior to randomization

The presence of heart failure will be assessed, and when present, classified according to the NYHA scale. NYHA classification will be determined by investigative center personnel and documented on the “New York Heart Association Classification” form. The NYHA classification scheme is detailed in Appendix III.

Quality of Life

Following determination of eligibility and within 14 days prior to randomization

The SF 12 and EuroQol (Appendix II) questionnaires will be completed by the patient to assess quality of life.

Pre-intervention Existing STS Registry Data Extraction (collected by sites if not participating in STS or for patients randomized to PCI group)

Angiogram

Data partially extracted from the STS Registry database

Data regarding the coronary anatomy, including the number of lesions, degree of coronary obstruction and SYNTAX score will be extracted from the STS registry database.

Demographics

For all patients screened, the date of birth, race, ethnicity, sex, and insurance will be captured.

Medical History

Data partially extracted from the STS Registry database

Information pertaining to the medical history, with particular focus on cardiovascular history, will be extracted from the STS registry database. The data collection includes, but is not limited to previous myocardial infarction and coronary revascularization, AICD and pacemaker therapy, stroke and other comorbidities such as diabetes, dialysis and peripheral vascular disease. Information regarding the current cardiac condition is also captured, including symptoms and severity of cardiac disease and the patient's current height and weight.

Laboratory Assessment

Data partially extracted from the STS Registry database

Data regarding the following laboratory values prior to index coronary revascularization will

- CK MB (creatinine kinase- myocardial band) and/or Troponin I or T (ng/mL)
- Hematocrit (%)
- Creatinine (mg/dL)

Treatment Intervention

The assigned study coronary revascularization intervention (or first revascularization intervention, for staged procedures) are *recommended to be performed within 72 hours post randomization, and must be performed within 14 days following randomization*. (See Randomization section)

Procedural and Peri-Procedural STS Registry Data Extraction (collected by sites if not participating in STS or for patients randomized to PCI group)

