A decision to stop the trial for safety reasons will be based on the result of the interim analysis as well as other supporting evidence that either arm of the trial poses unacceptable risk to patients. Should the data suggest that the composite rate of death, stroke or MI is significantly higher in one group than the other at the interim analysis (with a p-value of ≤ 0.0031), additional analyses and sub-group analyses will be conducted to supplement this information including investigation of site effects, adherence to the guideline-directed medical therapy, and other ad-hoc pertinent analyses as discussed and agreed upon with the DSMB.

Analysis Plan

The primary analysis will be an intent-to-treat analysis that will include all randomized participants regardless of treatment actually received or follow-up schedule. All hypothesis testing will be conducted using two sided tests at $\alpha = 0.05$.

Univariate Analysis

All outcome measures will be described in a univariate analysis. For continuous variables means and standard deviations will be calculated. For discrete and dichotomous variables, contingency tables will be used.

Analysis of Primary Endpoint

The primary endpoint of this study will be MACCE defined as all-cause mortality, myocardial infarction (MI), stroke, or unplanned revascularization over a minimum of 5 years of follow-up after randomization. Overall time to first event will be estimated using Kaplan-Meier curves. Survival time will be defined as the time (in months) between randomization and the occurrence of MACCE. To compare the HCR arm with the PCI arm we will use a stratified log-rank statistic using the stratification variables from the randomization procedure. A Cox proportional hazards model with treatment and stratification factors as covariates will be used for the multivariate analysis of the time to first MACCE. The assumption of proportionality will be tested prior to fitting the model. If the proportional hazards assumption is not met, the extended Cox model will be used. Hazard ratios and their 95% confidence intervals will be computed. Survival will be included in the analysis as censored if they are alive and free of

MACCE at the end of the study. Although we do not anticipate interactions between treatment and stratification factors, formal tests for interactions will be assessed using proportional hazards models.

Analysis of Secondary End-points

Secondary outcomes of the study will be analyzed as follows:

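### The primary MACCE analysis adjusts for no baseline variable beyond the stratification factors: a cheap efficiency gain is left unused, provided the added covariates are captured before randomization and alike in both arms

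*Combined protocol and SAP*

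**What the plan says.** Under Analysis of Primary Endpoint, the arms are compared by a log-rank statistic stratified by the randomization variables. For the multivariate analysis of time to first MACCE, "A Cox proportional hazards model with treatment and stratification factors as covariates will be used". The section on randomization (Treatment Assignments) gives three stratification factors: center, PCI of non-LM or non-LAD vessels in the prior 90 days, and vessels treated in three levels. No further covariate is named for the primary endpoint.

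Other baseline variables are recorded:

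- Angina (CCSC) class, NYHA class and quality of life carry the timing "Following determination of eligibility and within 14 days prior to randomization".
- Date of birth and sex are captured for all screened patients.
- Medical history covers items such as "previous myocardial infarction and coronary revascularization, AICD and pacemaker therapy, stroke and other comorbidities such as diabetes".
- SYNTAX score and creatinine are also listed.

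The Data Collection Schedule places demographics, history, angiogram and laboratory items under Screening & Randomization, with both a site column and a registry column. The Data Collection text is less uniform. It puts anatomy, history and laboratory data under STS registry extraction, with collection by the site for non-STS centers and for patients randomized to PCI. Laboratory values are tied to the index procedure, not to randomization.

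**The concern.** About three quarters of patients are expected to remain event-free at 5 years. In a Cox model, leaving out strong predictors then pulls the estimated log hazard ratio toward zero and lowers the test statistic. Pre-specified adjustment for true baseline predictors recovers that loss, reduces the effect of chance imbalance and leaves the type I error at its nominal level. The trial is sized at 80% power, so a few points gained from data already being collected would be worth having. A covariate list fixed now also prevents later dispute over which adjusted analysis counts.

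**Working it through.** **Inputs from the documents (Power and Sample Size; Abstract).** "two sided type I error fixed at 0.05"; 80% power; "5-year MACCE rate in the PCI group of approximately 25" percent; "expected 5-year MACCE relative rate reduction in the HCR group of" at least 20%; "minimum follow-up of 5 years, 2-year enrollment period with uniform enrollment"; "drop-in and drop-out rates of approximately 0.5% and 2% respectively, annually"; 15% loss to follow-up; 1:1 allocation; 530 events or 2354 patients.

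**Step 1: the plan's own figure.** Rates of 25% and 20% at 5 years give a hazard ratio of ln(0.80)/ln(0.75) = 0.776. A Markov log-rank calculation with these inputs gives N = 2336 with the crossover directions as written and 2353 with them reversed, so 2354 reproduces. The same model gives about 559 to 568 events rather than 530; however, 2354 × (25% + 20%)/2 = 529.65, which matches 530. With 530 events, 80% power corresponds to a hazard ratio of exp(−2 × 2.802/√530) = 0.784, where 2.802 = 1.960 + 0.842. No adjustment beyond the stratification factors is used to reach 80%.

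**Step 2: gain expressed as variance explained.** Power = Φ(2.802/√(1 − R²) − 1.960). The R² values are assumptions.

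| R² | 2% | 5% | 10% | 12.6% | 20% |
|---|---|---|---|---|---|
| Power | 80.8% | 82.0% | 84.0% | 85.0% | 88.0% |

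**Step 3: gain expressed as a prognostic score in a Cox model.** Let the added covariates form a normal score. Hold the marginal 5-year risks at 25% and 1 − 0.75^0.784 = 20.2%, solve for the conditional hazard ratio, and take power = Φ(|ln HR| × √530/2 − 1.960). For a score with hazard ratio 1.65 per SD the conditional hazard ratio is 0.7774, so 0.2518 × 11.51 − 1.960 = 0.938 and Φ = 82.6%. The last column is the gain in 2500 simulated trials per setting (2354 patients, about 532 events, Cox with and without the score).

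| Assumed HR per SD | C-index | Conditional HR | Power | Simulated gain |
|---|---|---|---|---|
| 1.22 | 0.55 | 0.783 | 80.4% | not run |
| 1.35 | 0.59 | 0.782 | 80.9% | +0.8 points |
| 1.65 | 0.63 | 0.777 | 82.6% | +2.4 points |
| 2.0 | 0.68 | 0.770 | 85.2% | +4.2 points |
| 2.7 | 0.74 | 0.755 | 90.0% | +10.0 points |

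The simulation assumes proportional hazards and leaves out crossover, loss to follow-up and the stratification factors. The C-index therefore stands for what the new covariates add beyond those factors.

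**Step 4: what happens if a covariate is captured differently by arm.** Null simulation: 2354 patients, 5 years, three binary comorbidities, each with 35% prevalence and hazard ratio 1.6, 1500 runs. All of these are assumptions.

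| Capture, HCR / PCI | Type I error, adjusted | Apparent HR under the null |
|---|---|---|
| 95% / 95% | 4.9% | not reported |
| 95% / 85% | 8.3% | 0.96 |
| 95% / 75% | 18% | 0.91 |

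The unadjusted test stays at about 5% in all three cases. Under-recorded comorbidity in the PCI arm makes those patients look lower-risk than they are, and the model credits the difference to HCR.

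**Step 5: which covariates are safe.** CCSC and NYHA class are dated before randomization for everyone. Age and sex are captured for all screened patients and do not depend on who records them. Diabetes, prior MI and SYNTAX score are listed at screening in the schedule, but the Data Collection text lets their source depend on the assigned arm. Creatinine need only precede the index procedure, and the first procedure may take place up to 14 days after randomization.

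**The case against.** The strongest reply has four parts.

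- *The plan already adjusts.* A reader might infer from the Cox sentence that no prognostic variable is used at all. The documents do not support that: center, prior PCI and vessels treated are baseline factors, vessels treated reflects the extent of disease, and both the stratified log-rank test and the Cox model use them. This stands.
- *Power is adequate as planned.* A reader might also infer that the trial is underpowered without adjustment. It is not shown to be: the stated N reproduces, and the Abstract defends 80% by calling its loss and crossover estimates conservative. This stands; the point concerns efficiency only.
- *The gain is assumed.* The documents contain no C-index, R² or covariate effect on MACCE, so a flat claim of 2 to 5 points would be unsupported. The simulation is also simpler than the trial, and the Background reports similar MACCE for 12 months followed by divergence, which is not proportional hazards. This stands, and is why the size is given as a range.
- *Adjustment could harm.* It is tempting to say that adjustment leaves the type I error unchanged and needs only a change of wording. That holds for values fixed before randomization and captured alike in both arms. In an open-label trial where history and laboratory data may come from the registry in one arm and the site in the other, Step 4 shows that it can fail. The schedule's screening columns leave the extent uncertain, so this limits the covariate list; it does not defeat the proposal.

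**Conclusion.** A cheap improvement, not an error. The primary MACCE analysis uses no baseline variable beyond its three stratification factors, although other likely predictors are recorded. With the prognostic strength of the added covariates assumed, the gain from 80% power is about 0.4 points at a C-index of 0.55 and about 10 points at 0.74. A gain of 2 to 5 points requires a C-index of about 0.62 to 0.68, or R² of about 5% to 12.6%, beyond the stratification factors. The short list that is safe on the documents as written (age, sex, CCSC, NYHA) may sit toward the lower end. The benefit is conditional on identical, pre-randomization capture in both arms; without that, the current analysis is the safer one.

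**What to change.** Before any comparative data are seen, amend Analysis of Primary Endpoint as follows.

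1. Specify a Cox model with treatment, the stratification factors and a short fixed list: age, sex, CCSC class and NYHA class. Keep center, for example as Cox strata or a frailty term. Since angina and heart failure are classed only when present, give their absence its own level, distinct from missing.
2. Add diabetes, prior MI and SYNTAX score only if, in both arms, they are taken from the site screening form completed before randomization, and not from the STS registry in one arm and the site in the other.
3. Leave out creatinine unless a pre-randomization value is used.
4. State whether the adjusted treatment test is the primary test, and report the stratified log-rank result alongside. If the adjusted test is primary, state what it becomes when the plan's provision for an extended Cox model applies.
5. Give one rule for missing baseline values, applied without regard to arm. The Missing Data section deals with loss to follow-up and names no rule for baseline covariates.

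The cost is analysis-plan wording for the short list, plus a check of the data source for the optional covariates. The downside is that the hazard ratio becomes conditional on the covariates, and any covariate captured differently by arm would bias the test.
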